University of Nottingham

Gut Imaging for Function & Transit in Cystic Fibrosis Study 1

Study protocol 1 September 2018, NCT03566550

Brief Summary

Many people with Cystic Fibrosis (CF) are troubled by symptoms from their stomach and bowels: their gastrointestinal (GI) tract. Symptoms affect quality of life and can also reduce people's ability to digest enough calories to remain healthy, leaving them undernourished and less able to deal with other health problems such as infection.

Clinical tests to assess bowel function are limited. Many tests involve inserting a sensor or camera into the bowel, so they are not suitable for long periods, and can be uncomfortable. In Nottingham the investigators have developed imaging scans which can assess how someone's digestion works without any invasive device. The type of scanning the investigators use is called Magnetic Resonance Imaging, or MRI.

The purpose of this study is to see if those scanning methods can be used in people with CF to understand their digestion and any problems they have.

Detailed Description:

This is a small pilot study to establish that differences in digestion between people with and without CF can be quantified by repeated MR scans in fasted participants in response to standardised meals.

Participants will complete questionnaires on gastrointestinal function and symptoms: the PAC-SYM questionnaire, validated to assess symptom burden in adults with chronic constipation; and the CF abdomen questionnaire, developed in German for use in young people and adults with cystic fibrosis.

After this, participants only need to attend one study day at the Sir Peter Mansfield Imaging Centre. On this day they will be asked to withhold any medicines specifically targeted to alter bowel habit. This shall include laxatives but not enzyme

replacement therapy. They should attend on the study day having fasted since waking, other than water for essential medicines.

They will have their first MRI scan fasted. After the scan they will eat a standard test meal, and be scanned again first at half hour, then hour intervals until six hours after the first meal. The final scan will constitute the end of the study for each participant. Each session in the MRI scanner will last around 15 minutes. After each scan they will score their abdominal pain, bloating and flatulence symptoms on a Likert scale. In between scans, participants will have access to a lounge with wi-fi and a television.

Infection control requirements mean that the investigators are unable to scan more than one patient with CF on a single day. Patient scans will alternate with those of a Control participant. The investigators will aim to frequency match Controls with Patients for age and gender.

Study Design

Study Type: Observational

Actual Enrollment: 24 participants

Observational Model: Case-Control

Time Perspective: Cross-Sectional

Official Title: A Case-Control, Observational Study of the Postprandial Changes in Magnetic Resonance Imaging Parameters of Gastrointestinal Function and Transit in People With Cystic Fibrosis

Actual Study Start Date: September 4, 2018

Actual Primary Completion Date: February 20, 2019

Actual Study Completion Date: February 20, 2019

Group/Cohort	Intervention/treatment
CF people with cystic fibrosis	Diagnostic Test: MRI scans Repeated MRI scans imaging digestion of standard meals
Control people without cystic fibrosis	Diagnostic Test: MRI scans Repeated MRI scans imaging digestion of standard meals

Outcome Measures

Primary Outcome Measures:

1. orocaecal transit time [Time Frame: 1 day of scanning] - time taken after eating for ingested food to be identifiable in the caecum on MRI

Secondary Outcome Measures:

1. gastric volume [Time Frame: 1 day of scanning] - volume of stomach at each time point of digestion to measure speed of gastric emptying
2. small bowel water content (corrected for body surface area) [Time Frame: 1 day of scanning] - volume of water content in small bowel representing secretions
3. colonic volume (corrected for body surface area) [Time Frame: 1 day of scanning] - volume of colon representing ease of chyme passage through colon

4. gastrointestinal symptoms [Time Frame: 1 day of scanning] - gastrointestinal symptoms as measured by questionnaires to monitor relationship with outcomes measured by MRI

Other Outcome Measures:

1. T1 relaxation time of ascending colon chyme [Time Frame: 1 day of scanning] - An approximate measure of water content in chyme present in the ascending colon
2. Fat fraction of the ascending colon chyme [Time Frame: 1 day of scanning] - A measure of fat content in chyme present in the ascending colon

Eligibility Criteria

Ages Eligible for Study: 12 Years to 40 Years (Child, Adult)

Sexes Eligible for Study: All

Accepts Healthy Volunteers: Yes

Sampling Method: Non-Probability Sample

Study Population

Nottingham and surrounding towns

Inclusion Criteria:

- Age 12 - 40 years
- Capacity to consent, or to understand the requirements of the study where parental consent is needed

PATIENTS: confirmed diagnosis of Cystic Fibrosis, either by sweat test or genetic testing; to reduce heterogeneity, we will only enrol homozygous CF patients with the most common CFTR mutation, p.Phe508del

CONTROLS: no clinical evidence or suspicion of Cystic Fibrosis

Exclusion Criteria:

Measurement of Forced Expiratory Volume in 1 second (FEV1) of <40% predicted using Global Lung Initiative criteria, according to clinical records

Contra-indication to MRI scanning, such as embedded metal, pacemaker

Unable to stop medications directly prescribed to alter bowel habit, such as laxatives or anti-diarrhoeals, on the study day

Previous resection of any part of the gastro-intestinal tract apart from appendicectomy or cholecystectomy. Surgical relief of distal intestinal obstruction syndrome or neonatal ileus will be permitted unless clinical records show excision of intestine >20cm in length.

Intestinal stoma

Diagnosis of inflammatory bowel disease or coeliac disease confirmed by biopsy

Gastrointestinal malignancy

Unable to comply with dietary restrictions required for the study

Statistical analysis plan

Data will be summarised through descriptive statistics. Differences between Patient and Control data will be tested using non-parametric methods. The software used will be GraphPad Prism version 7.0 or later, or SPSS version 21 or later, under licence to the University of Nottingham.

The primary and secondary outcomes will be compared firstly between CF patients and the non-CF controls using a t-test (for normally distributed variables) or a Mann-Whitney U test (for non-normally distributed data). We will then explore the association between the results of the symptom questionnaires and the MRI findings. We will compare MRI parameters such as OCTT, small bowel water and colonic volume against both the total CF Abdomen-Score and against the score for individual domains. An example of the latter would be comparing OCTT with the domains of “constipation” & “too much time spent on the toilet” from the CF Abdomen-score. We will compare these using a t-test or Mann Whitney U test, where the MRI parameter is a binary or categorical variable, and Pearson or Spearman’s correlation coefficient for continuous MRI parameters.

Where data is missing, through participant withdrawal or technical failure (e.g. scanner breakdown), an imputed value will be assigned which will be the median value for that parameter of other participants in the participant group (Patient/Control) at that time point.

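### The plan commits to neither a count of usable scans nor an estimate of the CF-Control difference with its uncertainty, though the pilot's stated aims call for both

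*Combined protocol and SAP*

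**What the plan says.** The purpose is stated twice. The Brief Summary, in lay terms: "The purpose of this study is to see if those scanning methods can be used in people with CF to understand their digestion"; the sentence goes on to include patients' digestive problems. The Detailed Description, in technical terms: "This is a small pilot study to establish that differences in digestion between people with and without CF can be quantified by repeated MR scans".

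Outcome Measures lists seven outcomes:
- primary: orocaecal transit time (OCTT), defined as "time taken after eating for ingested food to be identifiable in the caecum on MRI";
- secondary: gastric volume ("volume of stomach at each time point of digestion to measure speed of gastric emptying"), small bowel water content, colonic volume and gastrointestinal symptoms;
- other: T1 relaxation time and fat fraction of ascending colon chyme.

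All are physiological measures or symptoms.

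The Statistical analysis plan opens with "Data will be summarised through descriptive statistics". It then says "The primary and secondary outcomes will be compared firstly between CF patients and the non-CF controls using a t-test" or a Mann-Whitney U test, followed by an exploration of MRI findings against symptom scores. Where a value is missing through withdrawal or technical failure, "an imputed value will be assigned which will be the median value for that parameter of other participants in the participant group" at the same time point.

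**The concern.** The study day is demanding: a fasted scan, a test meal, then repeat scans until six hours after the meal. How many people with CF complete it, and how many scans give a readable value for each parameter, is direct evidence on whether the methods can be used in this population. The plan does not commit to reporting either. A withdrawn participant or failed scan enters the comparison as a typical value for the group.

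The second aim has a parallel gap. To quantify a difference is to estimate it and say how precisely. The plan describes each group and tests between groups, but does not commit to an estimated difference or an interval. In a study of 24 people, a P value alone says little about how large a difference the data support or exclude. If values have been median-filled, the P value is also too small on average.

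**Working it through.** The documents state no power, feasibility or precision figure, so there is none to reproduce.

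**Inputs**
- From the documents: 24 participants in total (Study Design); t-test or Mann-Whitney U test, and own-group median imputation (Statistical analysis plan).
- Assumed, because the documents do not say: 12 per group, two-sided 5% level, normally distributed data with equal SDs, and the numbers of missing values shown below.

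**1. Aims against planned outputs**

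| Aim | Evidence it calls for | What the plan commits to |
|---|---|---|
| Methods can be used in CF | Scans completed, scans readable, participants with OCTT determinable | None named |
| Differences can be quantified | Estimated difference with its uncertainty | Group descriptions and tests |

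**2. What a usability count could show.** Exact (Clopper-Pearson) 95% limits for x of n participants are the Beta(x, n−x+1) quantile at 0.025 and the Beta(x+1, n−x) quantile at 0.975. For x = n the lower limit is 0.025^(1/n), so 12/12 gives 0.025^(1/12) = 0.735.

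| Participants with usable scans | Exact 95% CI |
|---|---|
| 12/12 | 73.5% to 100% |
| 11/12 | 61.5% to 99.8% |
| 10/12 | 51.6% to 97.9% |
| 9/12 | 42.8% to 94.5% |

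These intervals are wide but informative. Once missing values are filled, all four cases enter the comparison with 12 values.

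**3. Precision of the comparison with complete data.** The half-width of the t-based 95% CI is t(0.975, 22) × √(2/12) = 2.074 × 0.408 = 0.85 SD. The mean half-width of the Hodges-Lehmann interval was 0.88 SD by simulation. Simulated Mann-Whitney power for a true 1 SD shift is about 61%, so such a difference is missed about 39% of the time (100 − 61). The t-test has about 65% power for the same shift.

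**4. Effect of median filling when there is no true difference.** In 40,000 simulated data sets per row, k of 12 values in each group were replaced by the median of that group's remaining values.

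| Filled per group | t-test error | Mann-Whitney error | Mean within-group SD (true value 1) |
|---|---|---|---|
| 0 | 5.0% | 4.3% | 0.98 |
| 1 | 7.2% | 7.3% | 0.93 |
| 2 | 10.4% | 11.8% | 0.88 |
| 3 | 14.6% | 18.0% | 0.83 |

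Filled values sit at the centre of the group, so the SD shrinks while the test still counts 12 observations per group. A t-test on the observed values alone stays near 5% in every row. If only the CF group has 3 of 12 filled, the error rates are about 9.5% (t-test) and 10% (Mann-Whitney).

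**The case against.** A reader might infer that the pilot cannot answer its own question, or that imputation hides the failures. The documents support neither.

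- The purpose sentence is from a lay summary and can be read as asking whether the scans are useful for understanding digestion in CF, not what their success rate is. The Detailed Description gives the operational aim, and the outcomes, group comparisons and symptom analyses address it. This stands.
- Missing values have to be identified before they can be filled, so the failure count survives. Nothing says descriptive statistics will be produced only after imputation, or that usability will be judged from a completed data table. This stands too: the gap is a missing commitment, not concealment.
- The imputation rule covers withdrawal and technical failure, with scanner breakdown as its example, and is silent on unreadable images. Equipment downtime says nothing about whether the method suits people with CF, so a single failure count would mix two things. This changes the fix.
- Naming tests does not exclude interval estimates, and no text says that a non-significant result would be read as no difference. True, but an analysis plan is there to commit to the output its aim needs.
- The power figure reflects sample size, which the fix does not alter. Also true. It shows why a P value alone is a poor summary here, not that the sample size is wrong.

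**Conclusion.** The point holds as a reporting and analysis gap, not as a mismatch between aim and design. Usability may go unreported, and the quantification aim rests on tests that are imprecise at this size and become anti-conservative once values are median-filled.

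The precision and power figures (half-width about 0.85 SD; about 61% Mann-Whitney power at 1 SD) depend on the assumed 12/12 split and normal data. The error rates (roughly 7% with one value filled per group, rising to 15% to 18% with three) depend also on the assumed amount of missing data. The documents give no missingness rate; if nothing is missing, the imputation part has no effect. The absence of a planned usability count and of a planned interval estimate depends on none of these assumptions.

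**What to change.** **Usability table, by group and before imputation.** Report:
- scheduled scans completed;
- scans giving a readable value for each parameter;
- participants with OCTT determinable.

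Count an imputed value as not obtained. List equipment breakdown separately from participant or image-quality failure. For OCTT, also separate a participant whose meal had not reached the caecum by the last scan from one whose scans failed, since the former is a finding about transit. Give exact 95% CIs for participant-level proportions only; repeated scans in one person are not independent, so the scan counts should stay descriptive.

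**Estimates for each CF-Control comparison.** From observed data, report the estimated difference with a 95% CI beside the P value. Examples are a Hodges-Lehmann difference for volumes and, for OCTT, a rank-based probability that a CF patient's value exceeds a Control's. If the median-filled analysis is kept, show it beside the observed-data result.

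**Cost.** One extra table and a few interval calculations on data already collected; no new scans or participants. Enrolment is complete, but both changes can still be made at analysis and reporting, labelled as additions to the plan. The downside is that failures become visible and the intervals will be wide.

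### Controls are frequency matched on age and gender, but the group comparison uses neither factor: a modest loss of power if matching works, and no protection from bias if it falls short

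*Combined protocol and SAP*

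**What the plan says.** - **Matching** (Detailed Description): "The investigators will aim to frequency match Controls with Patients for age and gender". No age bands, tolerance or balance check are given.
- **Sampling and age range** (Eligibility Criteria): "Ages Eligible for Study: 12 Years to 40 Years (Child, Adult" and "Sampling Method: Non-Probability Sample".
- **Size** (Study Design): "Actual Enrollment: 24 participants". The split between groups is not stated. The nearest guide is in the Detailed Description: "Patient scans will alternate with those of a Control participant".
- **Analysis** (Statistical analysis plan): "The primary and secondary outcomes will be compared firstly between CF patients and the non-CF controls using a t-test", or by "a Mann-Whitney U test (for non-normally distributed data". Age and gender do not appear anywhere in that section.
- **Body size** (Outcome Measures): small bowel water and colonic volume are corrected for body surface area. The primary outcome, orocaecal transit time (OCTT), and gastric volume are not.

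**The concern.** The design treats age and gender as worth balancing; the analysis then proceeds as if the groups were two unrelated random samples. There are two consequences, and both require age or gender to be related to the outcome.

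1. **Matching works.** Variation due to age and gender largely cancels from the difference between groups but stays in the pooled SD. The standard error is too large and the test rejects too seldom. With 24 people, the plan bears the recruitment cost of matching and forgoes part of its benefit.
2. **Matching falls short.** The crude difference carries the remaining imbalance. This is possible because matching is an intention rather than a rule, ages run from 12 to 40, and the sample is neither randomised nor drawn by probability sampling.

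**Working it through.** **Inputs.** From the documents: 24 participants, ages 12 to 40, matching on two factors, unadjusted two-sample tests. The plan gives no alpha, power, SD, effect size or R², so it has no figure to reproduce. Assumed: 12 per group, two-sided 5%, outcome SD 1, R² from 0 to 0.3 divided 3:1 between age and gender, ages uniform over 12 to 40. The true difference is set at 1.2 SD because that is what 12 v 12 detects with 80% power (minimum detectable difference 1.197 SD).

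**Step 1: matching works.** The crude standard error is about √(2/12) = 0.408 SD, but the true sampling SD is about 0.408 × √(1 − R²). The crude standard error is therefore too large by a factor 1/√(1 − R²). Adjustment moves the critical value from t(22) = 2.0739 to t(20) = 2.0860, so the ratio of adjusted to crude 95% interval width is √(1 − R²) × 2.0860/2.0739 = 1.006 × √(1 − R²). Type I error and power come from simulation, with gender balanced and ages matched closely (exactly balanced for the type I error at R² = 0.05).

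| R² | Crude SE ÷ true SD | Adjusted ÷ crude width | Crude t-test type I error | Power, crude v adjusted |
|---|---|---|---|---|
| 0 | 1.00 | 1.006 | about 5% | 80% v 80% |
| 0.05 | 1.03 | 0.98 | 4.3% | 81% v 82% |
| 0.1 | 1.05 | 0.95 | 4.1% | 81% v 83% |
| 0.2 | 1.12 | 0.90 | 3.1% | 83% v 88% |
| 0.3 | 1.20 | 0.84 | 2.1% | 84% v 92% |

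Repeat simulations agreed to about one percentage point. The Mann-Whitney test is conservative in the same way (type I error about 2% to 3% at R² = 0.2). Under exact balance, adjustment breaks even at R² = 1 − (2.0739/2.0860)² = 0.012.

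**Step 2: matching falls short.** Take one group 5 years older, with ages capped at 40. The cap reduces the realised gap to 5 − 5²/(2 × 28) = 4.55 years. The SD of age is 28/√12 = 8.08 years, so the gap is 0.563 SD of age. The crude bias is 0.563 × √(0.75 × R²):

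- R² = 0.1: 0.563 × 0.274 = 0.15 SD
- R² = 0.2: 0.563 × 0.387 = 0.22 SD (about 0.21 to 0.22 in simulation)
- R² = 0.3: 0.563 × 0.474 = 0.27 SD

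Adjusted bias was about 0 throughout. A different imbalance (0.5 SD of age plus two extra participants of one gender) gave crude bias of 0.17, 0.25 and 0.30 SD at the same R² values, and again about 0 after adjustment.

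**Step 3: the price of adjusting.** When the groups are balanced and R² = 0, adjustment costs less than one point of power. With the nominal 5-year gap and R² = 0, group and age are correlated, and power falls from about 80% crude to about 75% adjusted.

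**The case against.** **R² is unknown.** This stands. The documents relate neither factor to any outcome, and matching on age and gender is too routine a choice to be evidence of a large R². At 0.05 or below the gain is negligible, and that is as consistent with the documents as a gain that matters.

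**Frequency matching already makes the crude comparison adequate.** This is true of the point estimate when matching succeeds. It does not cover the standard error, or matching that is missed.

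**Body surface area correction already deals with it.** In part: it may absorb some of an age or gender effect on small bowel water and colonic volume. It does nothing for OCTT or gastric volume.

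**The simple tests are only a first step.** What follows them in the Statistical analysis plan is the relation between symptom scores and MRI findings, not an adjusted group comparison.

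**It is a small pilot.** That limits the weight of the point. But the stated purpose is to show that differences can be quantified, and an adjusted estimate serves that purpose.

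**Stronger readings that the documents do not support.**

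- A reader might infer that the planned test is invalid or that its reported intervals are wrong. With good matching the test is valid and errs on the cautious side, and the plan promises tests, not intervals.
- A reader might infer that matching failed. The documents report no group ages; the 5-year gap is only an illustration.
- A reader might infer a clearly inflated false-positive rate. Under the nominal 5-year gap it was only about 6%, and it depends on how the imbalance arises. The bias is the firmer result.
- A reader might infer that a paired test is needed. Matching is at group level, so there are no pairs to analyse.

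**Conclusion.** The mismatch between design and analysis is plain in the text, and worth correcting as a moderate point. With good matching, the loss is about 2 points of power at R² = 0.1, 5 at 0.2 and 8 at 0.3, and close to nothing at 0.05 or below. With a nominal 5-year age gap, the crude difference is biased by about 0.15 to 0.27 SD over R² of 0.1 to 0.3. All of these figures rest on an assumed R², 12 v 12, normally distributed outcomes and linear age effects. The direction of both effects is secure; their size in this study is not known from the documents.

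**What to change.** 1. Tabulate age and gender by group.
2. For the continuous volume outcomes, make the main comparison a pre-specified linear model with group, age (linear) and gender. Report the adjusted difference with its 95% CI.
3. For OCTT, which is read only at scan times up to six hours, pre-specify a rank-based or ordinal model with the same covariates. Place transit not seen by the last scan in the top rank or category, and report the result on that scale rather than in minutes.
4. Choose the form of model for each outcome in advance, so that no new data-dependent choice is introduced.
5. Keep the planned unadjusted tests as supporting analyses.

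**Cost.** No new data or visits are needed: both factors must be known in order to match, and SPSS, already named in the plan, fits the linear model. The statistical price is 2 of 22 degrees of freedom. It is cheap rather than free, because the loss in Step 3 applies if a sizeable age gap arises and the factors do not predict the outcome. Study Design already records completion of the study, so if the results have been seen, the adjusted analysis should be labelled post hoc.

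### The pilot is meant to show that CF–Control differences can be quantified, but the plan commits only to group summaries and tests, so the precision of the difference is not reported

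*Combined protocol and SAP*

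**What the plan says.** The Detailed Description calls this a small pilot, meant to establish that "differences in digestion between people with and without CF can be quantified by repeated MR scans". Study Design records "Actual Enrollment: 24 participants". Group sizes are not given. The only hints of a roughly equal split are that "Patient scans will alternate with those of a Control participant" and that Controls are frequency matched to Patients.

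The Statistical analysis plan has three sentences on the group comparison:

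- "Data will be summarised through descriptive statistics".
- "Differences between Patient and Control data will be tested using non-parametric methods".
- The primary and secondary outcomes are compared "using a t-test (for normally distributed variables) or a Mann-Whitney U test (for non-normally distributed data".

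The only effect measure named anywhere is a Pearson or Spearman "correlation coefficient for continuous MRI parameters". It concerns the association between symptoms and MRI findings, not CF versus Control. The documents give no significance level, no power or sample-size calculation, and no rule for interpreting a non-significant result.

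Two further features bear on the remedy. The primary outcome, OCTT, is the "time taken after eating for ingested food to be identifiable in the caecum on MRI". It can be read only at the scans, which are first half-hourly, then hourly, and stop six hours after the first meal. Values missing through withdrawal or technical failure are replaced by the median of the participant's own group at that time point.

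**The concern.** If the purpose is to show that a difference can be quantified, the natural output is the size of the difference and how well it is known. A Mann-Whitney p-value gives neither. Two group medians give a rough size by subtraction, but no interval for it. If means and SDs are reported, a reader could rebuild a t-based interval. If medians and quartiles are reported, no valid interval for the shift can be recovered. The plan does not say which descriptive statistics will be shown.

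What is at stake is how much can be learned from 24 people. In a study this small, a non-significant result fits both no difference and a substantial difference that was missed. An interval tells the reader how far apart those possibilities lie; a bare p-value does not. Anyone sizing a follow-up study from this pilot would need the same information.

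**Working it through.** The plan states no power, SD, effect size or significance level, so it has no figure to reproduce. The calculation below only shows how much information the missing interval would carry.

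**Inputs**
- Total of 24 participants, from Study Design.
- Split: not stated. 12 v 12 is assumed because Patient and Control scans alternate; 10 v 14 and 8 v 16 are shown as a range.
- Two-sided 5% level, normal data with equal SDs, and differences in SD units: all assumptions.

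**Interval half-width for a mean difference**

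Half-width = t(0.975, n1 + n2 − 2) × √(1/n1 + 1/n2), with t(0.975, 22) = 2.074.

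| Split | √(1/n1 + 1/n2) | Half-width (SD) |
|---|---|---|
| 12 v 12 | 0.408 | 0.85 |
| 10 v 14 | 0.414 | 0.86 |
| 8 v 16 | 0.433 | 0.90 |

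With 12 v 12, an observed difference of zero is compatible with true differences from −0.85 to +0.85 SD. An observed difference of 0.8 SD gives 0.8 ± 0.85, or −0.05 to 1.65 SD. That result is non-significant but plainly not evidence of no difference.

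For the Hodges-Lehmann shift, the 12 × 12 = 144 pairwise differences are sorted and the 38th from each end is taken as the limit. In 5,000 simulated studies the average half-width was 0.88 SD and coverage was 96%.

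**How often a real difference is non-significant**

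t-test power comes from the noncentral t distribution with 22 degrees of freedom and noncentrality d / 0.408. Mann-Whitney power is simulated on normal data.

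| True difference (SD) | t-test power | Mann-Whitney power |
|---|---|---|
| 0.5 | 22% | about 19% |
| 0.8 | 47% | about 43% |
| 1.0 | 65% | about 61% |

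The t-test reaches 80% power at 1.20 SD for 12 v 12, 1.21 SD for 10 v 14 and 1.27 SD for 8 v 16.

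At a true 0.8 SD, about 58% of simulated 12 v 12 studies were non-significant by exact Mann-Whitney. In about 89% of those, the upper limit of the Hodges-Lehmann interval still reached 1 SD or more. The interval would usually have shown the reader that the miss reflected imprecision.

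**Whether a plain shift estimate suits OCTT**

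The plan does not say what value is recorded when food has not reached the caecum by the last scan. As an illustration, suppose SD 1.5 h, a true shift of 1.5 h, mostly hourly scans, and late arrivals recorded as 6 h. None of these values comes from the documents.

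| Control mean | Controls past 6 h | CF past 6 h | Mean Hodges-Lehmann estimate | Coverage of 95% interval |
|---|---|---|---|---|
| 4 h | 1 − Φ(2/1.5) = 9% | 1 − Φ(0.5/1.5) = 37% | 0.99 h | 84% |
| 5 h | 1 − Φ(1/1.5) = 25% | 1 − Φ(−0.5/1.5) = 63% | 0.37 h | 35% |

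The true shift is 1.5 h in both rows. With many late arrivals, a plain shift is far too small and its interval far too confident.

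**The case against.** The strongest reply has four parts.

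- **The aim is partly feasibility.** The Brief Summary says the purpose is to see whether the scanning methods can be used in people with CF, and the Detailed Description speaks of what can be quantified. Group descriptives do quantify each group and allow a point difference. This stands. A reader might infer that the plan fails to answer its own question; the documents do not support that. What is missing is the precision of the difference.
- **The misreading is hypothetical.** A reader might also infer that the investigators will treat p>0.05 as no difference. No sentence says so, and no threshold or decision rule is set. This too stands: it is a risk in reporting, not a stated error.
- **The power figures only show that 24 is few.** The plan already calls itself a small pilot, and an interval does not add information. That is true, and the figures are not a complaint about the sample size. They show that the imprecision is large enough to need reporting.
- **A standard shift estimate does not suit the primary outcome, and repeated outcomes have no named summary.** This is correct and changes the remedy. Gastric volume, for example, is measured at every time point, so a single difference is undefined until a summary is chosen. Imputed group medians would also make any interval too narrow.

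These points limit the claim and shape the fix. They do not supply the missing estimate or interval.

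**Conclusion.** The point holds as a gap in the planned output. The planned tests are not made invalid by it, but as written they leave the precision of the CF–Control difference unreported for every outcome. Under 12 v 12, a two-sided 5% level and normal data, that unreported uncertainty is about ±0.85 SD, and it changes little across the splits examined (up to ±0.90 SD). A true difference of 0.8 SD would be missed more often than not.

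The SD-unit figures rest on assumptions about the split, level and distribution, because the documents give none of these. The OCTT figures are illustrative only; they support the choice of method and say nothing about what this study found. The change should be made, since it bears directly on what the pilot can conclude and needs no new data.

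**What to change.** 1. For OCTT and each secondary outcome, make the CF–Control difference with its 95% confidence interval the main result, and give the p-value second.
2. Match the estimate to the test: the mean difference with the t-test, the Hodges-Lehmann shift with the Mann-Whitney test.
3. For outcomes measured repeatedly, name one summary per participant and estimate the difference in that summary.
4. For OCTT, use an estimate and interval that allow for interval censoring between scans and right censoring at six hours, for example a difference in medians from an interval-censored survival model. Do not use a plain Hodges-Lehmann shift with late arrivals set to six hours.
5. Compute the intervals without counting group-median imputed values as observed data.
6. State that p>0.05 will not be reported as absence of a difference. No importance margin is needed for this.

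The cost is SAP wording, a little extra analysis (mainly the censored model for OCTT), and wide intervals that look less favourable than a bare p-value. Study Design records completion in February 2019, so the additions should be labelled as made after the plan.
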